2. LIST OF ABBREVIATIONS

Abbreviation	Definition
ACE	Angiotensin-converting enzyme
AE	Adverse Event
ARB	Angiotensin II receptor blockers
ATC	Anatomical Therapeutic Chemical Classification System
CCI	Charlson Comorbidity Index
CI	Confidence Intervals
CIOMS	Council for International Organizations of Medical Sciences
COPD	Chronic Obstructive Pulmonary Disease
DOAC	Direct Oral Anticoagulants
DVT	Deep Vein Thrombosis
EMA	European Medicines Agency
ENCePP	European Network of Centres for Pharmacoepidemiology and Pharmacovigilance
GEP	Good Epidemiological Practice
GPP	Guidelines for Good Pharmacoepidemiology Practices
GI	Gastrointestinal
HAS-BLED	Hypertension, Abnormal renal and liver function, Stroke, Bleeding history or predisposition, Labile international normalized ratio (INR), Elderly (> 65 years), Drugs or alcohol concomitantly
HIRA	Health Insurance Review and Assessment Service

PFIZER CONFIDENTIAL

HIRA-NPS	Health Insurance Review and Assessment Service-National Patient Sample
HR	Hazard Ratios
ICD-10	International Classification of Diseases, 10 th Revision
IQR	Interquartile Range
IEA	International Epidemiological Association
IRB	Institutional Review Board
ISPE	International Society for Pharmacoepidemiology
ISPOR	International Society for Pharmacoeconomics and Outcomes Research
LMWH	Low Molecular Weight Heparin
NDC	National Drug Code
NOAC	Non-vitamin K Antagonist Oral Anticoagulants
NSAIDs	Nonsteroidal Anti-inflammatory Drugs
NVAF	Non-Valvular Atrial Fibrillation
OAC	Oral Anticoagulant
PAC	Parenteral Anticoagulants
PASS	Post-Authorisation Safety Study
PE	Pulmonary Embolism
PPV	Positive Predictive Value
PS	Propensity Score
RCT	Randomized Controlled Trial
SD	Standardized Difference

SSRI	Selective serotonin reuptake inhibitors
STD	Standard Deviation
UFH	Unfractionated Heparin
VKA	Vitamin K Antagonist
VTE	Venous Thromboembolism

PFIZER CONFIDENTIAL

[figure not shown]

4. ABSTRACT

- **Protocol title**

Treatment patterns and clinical outcomes among venous thromboembolism patients treated with anticoagulants after the entry of non-vitamin K antagonist oral anticoagulants in Korea

- **Protocol version and date**

2.0, 27 Apr 2022

- **Rationale and background**

Venous Thromboembolism (VTE), which includes deep vein thrombosis (DVT) and pulmonary embolism (PE), is a major cause of morbidity, mortality and healthcare expenditure. Although the occurrence of VTE in the Asian population has been lower than that in Western populations, its incidence has been reported to have increased rapidly in recent years.

For pharmacologic treatment of patients with VTE without cancer, the American College of Chest Physicians (CHEST) guidelines recommend the use of Non-Vitamin K antagonist oral anticoagulants (NOACs) over Vitamin K Antagonists (VKAs), with supporting evidences suggesting that each NOAC (e.g., apixaban) is effective at preventing recurrent VTE. In more recent treatment guidelines for the management of VTE released by the American Society of Hematology (ASH), NOACs are still recommended over VKAs for the initial management of VTE. NOACs are classified as a new generation of anticoagulants with approved indications of the risk reduction of stroke and embolism in nonvalvular atrial fibrillation (NVAF) as well as prophylaxis and treatment of DVT and PE.

All NOACs became available as the first-line treatment of acute VTE in Korea after reimbursement expansion in May 2015. However, despite the increasing use of NOACs among VTE patients, there are still limited real-world evidence that assess treatment patterns as well as effectiveness and safety of the different anticoagulants especially among Asian population.

- **Research question and objectives**

Research question

- What is the real-world evidence of anticoagulant treatment for patients with VTE that can be found in the nationwide claims database in Korea?

The current study will take place in two phases:

Phase I involves a descriptive assessment of VTE patient characteristics and treatment patterns in Korea as well as detailed power calculations for comparative analyses.

Phase II involves analyses of comparative safety between each NOAC and warfarin. These analyses will be implemented if there is sufficient power to enable scientifically valid inferences.

Primary objectives of Phase I of the study

- To describe the sociodemographic and clinical characteristics of patients with VTE, overall and according to their index VTE treatment (parenteral anticoagulants [PAC] only, warfarin-based, NOAC-based) To describe index anticoagulant treatment patterns by investigating the utilization of different anticoagulants, treatment interruption, switches, discontinuations, and overall treatment duration

Primary objective of Phase II of the study

- To describe and compare the risk of clinical outcome (major bleeding) according to the specific type of OAC

[NOTE] Comparative analyses, especially NOAC vs NOAC direct comparisons, will be performed contingent on a feasibility assessment based on the descriptive analyses and the agreed opinion on scope after discussion with Eliquis Alliance Real World Data Review Committee.

Secondary objective of Phase I of the study

- To explore the relevant clinical events preceding treatment change from index anticoagulant
- **Study design**
 - Retrospective, observational, nationwide population-based cohort study

• **Population**

Study period

- 1 Mar 2012 to 31 Dec 2019

Inclusion criteria

- Incident VTE diagnosis in an inpatient or outpatient setting (International Classification of Diseases 10th Revision [ICD-10]: I26.0, I26.9, I80.2, I80.3) between 1 Mar 2013 and 30 Jun 2019.

- Received anticoagulation therapy (all medication codes for anticoagulants approved for VTE in Korea; unfractionated heparin [UFH], low molecular weight heparin [LMWH], warfarin, and NOACs) within 30 days of their VTE diagnosis (the index date will be defined as the date of treatment initiation with anticoagulants)
- Aged ≥ 18 years at index date

Exclusion criteria

- A record of VTE diagnosis within the 12-month period prior to the index VTE encounter
- Diagnosed with atrial fibrillation, atrial flutter, mechanical heart valve replacement or mitral stenosis anytime prior to index date
- Had a record of Inferior Vena Cava filter anytime prior to index date
- Received anticoagulation therapy within the 12-month period prior to index VTE encounter to restrict to new users of anticoagulation therapy
- Prescribed two different anticoagulants on the same index date to prevent exposure misclassification
- Had a record of pregnancy within the 9-month period prior to index date

Additional exclusion criteria for comparative analyses

- Had a record of active cancer, defined as first diagnosis of cancer with V code (a special code applied to patients with confirmed diagnosis of cancer by Korean Ministry of Health and Welfare for reimbursement for 5 years or longer if recurrent/metastatic) within the past 6 months of period prior to index date; or receiving anti-cancer treatment (chemotherapy, radiation therapy, or cancer-related surgery) under cancer diagnosis with V code within the past 6 months period prior to index date

Follow-up

- **Phase I of the study:** Patients will be followed-up from the index date until the earliest of in-hospital death or end of the study period (31 Dec 2019).
- **Phase II of the study:** Patients will be followed-up from the index date until the earliest of outcome occurrence (bleeding event), treatment discontinuation, switch to another anticoagulant, in-hospital death, or end of the study period (31 Dec 2019), where patients will be considered to have discontinued treatment when new prescription is absent within the 30-day grace period after the end of the former prescription.

- **Variables**

Exposure(s)

- Anticoagulant therapy (PAC [LMWH, UFH, others], NOACs [apixaban, dabigatran, rivaroxaban, edoxaban], warfarin).

Outcome(s)

- **Phase I of the study:** sociodemographic and clinical characteristics of patients with VTE, utilization of index anticoagulant treatment, treatment patterns (including treatment interruption, switching, complete discontinuation), overall treatment duration, and clinical events preceding first treatment change
- **Phase II of the study:** Primary or secondary diagnosis with major bleeding (by site: intracranial, gastrointestinal [GI], and other sites) after the index date

Covariate(s)

- Sociodemographics (age, sex) will be assessed on the index date. Clinical characteristics including comorbidities, previous use of medications, and the number of outpatient visits will be assessed within the 6-month period prior to the index date

- **Data sources**

- South Korea's Health Insurance and Review Assessment Service (HIRA) database

- **Study size**

- The estimated number of incident patients with VTE and no history of active cancer from the 2018 HIRA-National Patient Sample (HIRA-NPS) database is 1,465, where the HIRA-NPS database is a 3% random sample of the entire Korean population of 50 million. Based on this estimation, the projected number of patients with VTE from the entire Korean population (HIRA database) of 2018 is 48,828 (1,465 * 33.33).
 - Excluding period for patients with previous OAC treatment, VTE history or a history of active cancer was set to prior 3 months because HIRA NPS database used in sample size estimation was constituted of one-year data only.

1) Apixaban vs. warfarin

- Among the above-mentioned number of incident patients with VTE and no history of active cancer, those who newly initiated apixaban or warfarin was estimated to be 211 patients (14.4%; 211/1,465), where patients had no prescription for OACs and no history of VTE within the 3-month period prior to VTE diagnosis. From these 211 patients, there were 83 (39.3%) apixaban users and 128 (60.7%) warfarin users

(based on 2018 HIRA-NPS data). Hence, the projected number of patients with VTE who newly initiated OACs to be present in the HIRA database in a single year is 7,032 patients (apixaban 2,766; warfarin 4,266). As this study aims to utilize data from 2013 to 2019 (7 years), the final projected number of patients with VTE who newly initiated apixaban or warfarin from the HIRA database is 49,224 patients (apixaban 19,362; warfarin 29,862).

- Considering a 95% for a two-sided CI level (α -error=0.05) and 80% power, the sample size for the comparative safety study for major bleeding events was calculated based on the following components:
 - HR for major bleeding events from previous literature: 0.31-0.75
 - Overall probability of major bleeding events from previous literature: 1.19%
 - Proportion of apixaban users among patients with VTE from the 2018 HIRA-NPS database: 39.3% (83 apixaban users; 128 warfarin users).
 - 2,013 patients with VTE treated with apixaban or warfarin are required to detect at 5% α -error, and 80% statistical power, and HR of 0.31 by sample size calculations for survival analysis; alternatively (more conservative estimate), 33,340 patients with VTE treated with apixaban or warfarin are required to detect at 5% α -error, and 80% statistical power, and HR of 0.75 by sample size calculations for survival analysis.
 - As this study is expected to include 49,224 patients with VTE, with 19,362 patients treated with apixaban from the nationwide HIRA database, this study will have enough statistical power to test the hypothesis of the association between apixaban use and risk of bleeding events among patients with VTE.

2) Rivaroxaban vs. warfarin

- Among the above-mentioned number of incident patients with VTE and no history of active cancer, those who newly initiated rivaroxaban or warfarin was estimated to be 382 patients (26.1%; 382/1,465), where patients had no prescription for OACs and no history of VTE within the 3-month period prior to VTE diagnosis. From these 382 patients, there were 264 (69.1%) rivaroxaban users and 118 (30.9%) warfarin users (based on 2018 HIRA-NPS data). Hence, the projected number of patients with VTE who newly initiated OACs to be present in the HIRA database in a single year is 12,732 patients (rivaroxaban 8,799; warfarin 3,933). As this study aims to utilize data from 2013 to 2019 (7 years), the final projected number of patients with VTE who newly initiated rivaroxaban or warfarin from the HIRA database is 89,124 patients (rivaroxaban 61,593; warfarin 27,531).

- Considering a 95% for a two-sided CI level (α -error=0.05) and 80% power, the sample size for the comparative safety study for major bleeding events was calculated based on the following components:
 - HR for major bleeding events from previous literature: 0.77-1.19
 - Overall probability of major bleeding events from previous literature: 8.1%
 - Proportion of rivaroxaban users among patients with VTE from the 2018 HIRA-NPS database: 69.1% (264 rivaroxaban users; 118 warfarin users).
 - 6,630 patients with VTE treated with rivaroxaban or warfarin are required to detect at 5% α -error, and 80% statistical power, and HR of 0.77 by sample size calculations for survival analysis; alternatively (more conservative estimate), 14,967 patients with VTE treated with rivaroxaban or warfarin are required to detect at 5% α -error, and 80% statistical power, and HR of 1.19 by sample size calculations for survival analysis.
 - As this study is expected to include 89,124 patients with VTE, with 61,593 patients treated with rivaroxaban from the nationwide HIRA database, this study will have enough statistical power to test the hypothesis of the association between rivaroxaban use and risk of bleeding events among patients with VTE.

3) Edoxaban vs. warfarin

- Among the above-mentioned number of incident patients with VTE and no history of active cancer, those who newly initiated edoxaban or warfarin was estimated to be 184 patients (12.6%; 184/1,465), where patients had no prescription for OACs and no history of VTE within the 3-month period prior to VTE diagnosis. From these 184 patients, there were 57 (31.0%) edoxaban users and 127 (69.0%) warfarin users (based on 2018 HIRA-NPS data). Hence, the projected number of patients with VTE who newly initiated OACs to be present in the HIRA database in a single year is 6,132 patients (edoxaban 1,900; warfarin 4,232). As this study aims to utilize data from 2013 to 2019 (7 years), the final projected number of patients with VTE who newly initiated edoxaban or warfarin from the HIRA database is 42,924 patients (edoxaban 13,300; warfarin 29,624).
- Considering a 95% for a two-sided CI level (α -error=0.05) and 80% power, the sample size for the comparative safety study for major bleeding events was calculated based on the following components:
 - HR for major bleeding events from previous literature: 0.56-0.81
 - Overall probability of major bleeding events from previous literature: 8.5%

- Proportion of edoxaban users among patients with VTE from the 2018 HIRA-NPS database: 31.0% (57 edoxaban users; 127 warfarin users).
- 1,282 patients with VTE treated with edoxaban or warfarin are required to detect at 5% α -error, and 80% statistical power, and HR of 0.56 by sample size calculations for survival analysis; alternatively (more conservative estimate), 9,703 patients with VTE treated with edoxaban or warfarin are required to detect at 5% α -error, and 80% statistical power, and HR of 0.81 by sample size calculations for survival analysis.
- As this study is expected to include 42,924 patients with VTE, with 13,300 patients treated with edoxaban from the nationwide HIRA database, this study will have enough statistical power to test the hypothesis of the association between edoxaban use and risk of bleeding events among patients with VTE.

4) Dabigatran vs. warfarin

- Among the above-mentioned number of incident patients with VTE and no history of active cancer, those who newly initiated dabigatran or warfarin was estimated to be 155 patients (10.6%; 155/1,465), where patients had no prescription for OACs and no history of VTE within the 3-month period prior to VTE diagnosis. From these 155 patients, there were 26 (16.8%) dabigatran users and 129 (83.2%) warfarin users (based on 2018 HIRA-NPS data). Hence, the projected number of patients with VTE who newly initiated OACs to be present in the HIRA database in a single year is 5,166 patients (dabigatran 866; warfarin 4,299). As this study aims to utilize data from 2013 to 2019 (7 years), the final projected number of patients with VTE who newly initiated dabigatran or warfarin from the HIRA database is 36,162 patients (dabigatran 6,062; warfarin 30,093).
- Considering a 95% for a two-sided CI level (α -error=0.05) and 80% power, the sample size for the comparative safety study for major bleeding events was calculated based on the following components:
 - HR for major bleeding events from previous literature: 0.52-0.69
 - Overall probability of major bleeding events from previous literature: 1.4%
 - Proportion of dabigatran users among patients with VTE from the 2018 HIRA-NPS database: 16.8% (26 dabigatran users; 129 warfarin users).
 - 9,361 patients with VTE treated with dabigatran or warfarin are required to detect at 5% α -error, and 80% statistical power, and HR of 0.52 by sample size calculations for survival analysis; alternatively (more conservative estimate), 29,071 patients with VTE treated with edoxaban or warfarin are required to

detect at 5% α -error, and 80% statistical power, and HR of 0.69 by sample size calculations for survival analysis.

- As this study is expected to include 36,162 patients with VTE, with 6,062 patients treated with dabigatran from the nationwide HIRA database, this study will have enough statistical power to test the hypothesis of the association between dabigatran use and risk of bleeding events among patients with VTE.

[figure not shown]
- **Data analysis**

- Descriptive analysis will be conducted separately in two cohorts of non-cancer VTE and cancer VTE patients according to co-presence of active cancer.
- We will use descriptive statistics to describe the baseline sociodemographic and clinical characteristics of patients with VTE and present them as mean and standard deviation (STD) for continuous variables or counts with proportions for categorical variables. Significance test will be conducted between the three treatment groups of interest using analysis of variance for continuous variables and chi-square test for categorical variables.
- We will describe the utilization pattern of anticoagulant treatments among patients with VTE as counts with proportions. We will also estimate the treatment patterns (including treatment interruption, switches, discontinuation) and the overall treatment duration as median (interquartile range [IQR]) or mean (STD) by each index anticoagulant treatment. To identify potential reasons for treatment change, clinical events preceding the first treatment change will be measured within 30 days prior to the first date of treatment change.
- We will calculate the incidence of major bleeding overall and by site per 1,000 person-years based on the Poisson distribution. We will estimate propensity scores (PS) using multivariable logistic regression models for the likelihood of receiving each NOAC or warfarin, conditioned on baseline sociodemographic and clinical characteristics. We will use multivariable Cox proportional hazard regression models to estimate HRs with 95% CIs for the risk of major bleeding associated with each OAC use, as compared with other OAC, with the PS applied as inverse probability of treatment weights to minimize residual confounding bias and increase comparability between treatment groups.
- All analyses will be conducted using SAS Enterprise Guide 7.1 (SAS Institute Inc, Cary, NC), provided by HIRA through a virtual access machine.

- **Milestones**

- The results of this study are anticipated in Q2 2022. The expected completion date of preliminary analysis is Q3 2021 and the final report in Q3 2022. The milestones are dependent on receipt of requested dataset from HIRA.

PFIZER CONFIDENTIAL

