9.2.2. Exclusion criteria

Patients meeting any of the following criteria will not be included in the study:

1. Had a record of VTE diagnosis (ICD-10: I26.0, I26.9, I80.2, I80.3) within the 12-month period prior to the index VTE encounter.
2. Diagnosed with atrial fibrillation/flutter (ICD-10: I48), mechanical heart valve replacement (National Procedure Code: Z952, M6531, M6532, M6533, O1781, O1782,

O1783, O1791, O1792, O1793, O1797, O1794, O1795, O1796, O1798, O1799) or mitral stenosis (ICD-10: I05.0, I05.2) anytime prior to index date

3. Had a record of Inferior Vena Cava filter (National Procedure Code: O2045, M6650) anytime prior to index date
4. Received anticoagulatory therapy within the 12-month period prior to index VTE encounter to restrict to new users of anticoagulatory therapy.
5. Prescribed two different anticoagulants on the same index date to prevent exposure misclassification.
6. Had a record of pregnancy (ICD-10: O03-O07, O10-O14, O16, O20-O026, O28-O36, O41-O43, O46.8, O46.9, O61-O66, O67.8, O67.9, O69, O70-O75, O80-O92, O94-O99, P08, Z33-Z39) within the 9-month period prior to index date
7. Had a record of active cancer, defined as first diagnosis of cancer (ICD-10: C00-C97 [excluding non-melanoma skin cancer: C44]) with V code (V011, V027, V193, V194; a special code applied to patients with confirmed diagnosis of cancer by Korean Ministry of Health and Welfare for reimbursement for 5 years or longer if recurrent/metastasis) within the past 6 months of period prior to index date; or receiving anti-cancer treatment (chemotherapy, radiation therapy, or cancer-related surgery) under cancer diagnosis with V code within the past 6 months from index date (for Phase II of the study only). WHO-ATC codes and National Procedure Codes for anti-cancer treatment are shown in Table 1.

Table 1. WHO-ATC codes and National Procedure Codes for anti-cancer treatment

Anti-cancer treatment	WHO-ATC codes / National Procedure Codes
Chemotherapy	L01-04, H02AB02, H02AB04, H02AB06, H02AB07, H02AB09
Radiation therapy	HD051-HD059, HD061, HD071-HD073, HD080-HD089, HD091-HD093, HD110-HD115, HD121, HD150, HD160, HD211, HD212, HZ271

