8.3.2. Exclusion criteria

Patients meeting any of the following criteria will not be included in the study:

1. Had a record of VTE diagnosis (ICD-10: I26.0, I26.9, I80.2, I80.3) within the 12-month period prior to the index VTE encounter.
2. Diagnosed with atrial fibrillation/flutter (ICD-10: I48), mechanical heart valve replacement (National Procedure Code: Z952, M6531, M6532, M6533, O1781, O1782, O1783, O1791, O1792, O1793, O1797, O1794, O1795, O1796, O1798, O1799) or mitral stenosis (ICD-10: I05.0, I05.2) anytime prior to index date.
3. Had a record of Inferior Vena Cava filter (National Procedure Code: O2045, M6650) anytime prior to index date.
4. Received anticoagulatory therapy within the 12-month period prior to index VTE encounter to restrict to new users of anticoagulatory therapy.
5. Prescribed two different anticoagulants on the same index date to prevent exposure misclassification.
6. Had a record of pregnancy (ICD-10: O03-O07, O10-O14, O16, O20-O026, O28-O36, O41-O43, O46.8, O46.9, O61-O66, O67.8, O67.9, O69, O70-O75, O80-O92, O94-O99, P08, Z33-Z39) within the 9-month period prior to index date.

7. Had a record of active cancer, defined as first diagnosis of cancer (ICD-10: C00-C97 [excluding non-melanoma skin cancer: C44]) with V code (V011, V027, V193, V194; a special code applied to patients with confirmed diagnosis of cancer by Korean Ministry of Health and Welfare for reimbursement for 5 years or longer if recurrent/metastasis) within the past 6 months of period prior to index date; or receiving anti-cancer treatment (chemotherapy, radiation therapy, or cancer related-surgery) under cancer diagnosis with V code within the past 6 months from index date (for Phase II of the study only). WHO-ATC codes and National Procedure Codes for anti-cancer treatment are shown in below table.

Anti-cancer treatment	WHO-ATC codes / National Procedure Codes
Chemotherapy	L01-04, H02AB02, H02AB04, H02AB06, H02AB07, H02AB09
Radiation therapy	HD051-HD059, HD061, HD071-HD073, HD080-HD089, HD091-HD093, HD110-HD115, HD121, HD150, HD160, HD211, HD212, HZ271

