Diabetes without chronic complication	1	E10.0, E10.1, E10.6, E10.8, E10.9, E11.0, E11.1, E11.6, E11.8, E11.9, E12.0, E12.1, E12.6, E12.8, E12.9, E13.0, E13.1, E13.6, E13.8, E13.9, E14.0, E14.1, E14.6, E14.8, E14.9
Mild liver disease	1	B18, K70.0-K70.3, K70.9, K71.3-K71.5, K71.7, K73, K74, K76.0, K76.2-K76.4, K76.8, K76.9, Z94.4
Myocardial infarction	1	I21, I22, I25.2
Peripheral vascular disease	1	I70, I71, I73.1, I73.8, I73.9, I77.1, I79.0, I79.2, K55.1, K55.8, K55.9, Z95.8, Z95.9
Peptic ulcer disease	1	K25-K28
Rheumatologic disease	1	M05, M06, M32–M34, M31.5, M35.1, M35.3, M36.0
Diabetes with chronic complication	2	E10.2–E10.5, E10.7, E11.2–E11.5, E11.7, E12.2–E12.5, E12.7, E13.2–E13.5, E13.7, E14.2–E14.5, E14.7
Hemiplegia or paraplegia	2	G04.1, G11.4, G80.1, G80.2, G81, G82, G83.0-G83.4, G83.9
Any malignancy, including leukemia and lymphoma	2	C00–C26, C30–C34, C37–C41, C43, C45–C58, C60–C76, C81–C85, C88, C90–C97
Renal disease	2	I12.0, I13.1, N03.2-N03.7, N05.2–N05.7, N18, N19, N25.0, Z49.0–Z49.2, Z94.0, Z99.2
Moderate or severe liver disease	3	I85.0, I85.9, I86.4, I98.2, K70.4, K71.1, K72.1, K72.9, K76.5, K76.6, K76.7
AIDS/HIV	6	B20–B22, B24
Metastatic solid tumor	6	C77-C80

List of HAS-BLED	Score	ICD-10 codes

Hypertension	1	I10-I15
Abnormal renal function	1	N18.3, N18.4, N18.5, N19, Z94.0, Z99.2
Abnormal liver function	1	B15-B19, C22, D68.4, I98.2, I98.3, K70-K77, Z94.4
Stroke	1	I63, I69.3, G45.9
Bleeding history	1	Intracranial and GI: I60, I61, I62, I69.0, I69.1, I69.2, S06.4, S06.5, S06.6, S06.8, I85.0, I98.3, K22.11, K22.6, K22.8, K25.0, K25.2, K25.4, K25.6, K26.0, K26.2, K26.4, K26.6, K27.0, K27.2, K27.4, K27.6, K28.0, K28.2, K28.4, K28.6, K29.0, K31.81, K55.21, K62.5, K92.0, K92.1, K92.2 Other sites*: D62, H44.8, H35.72, H35.6, H31.3, H21.0, H11.3, H05.2, H47.0, H43.1, I31.2, N02.0-N02.9, N42.1, N83.1, N85.7, N92.0, N92.3, N93.0, N93.8, N93.9, M25.0, R23.3, R04.0, R04.1, R04.2, R04.8, R04.9, T79.2, T81.0, N95.0, R31.0, R31.1, R31.8, R58, T45.5, Y44.2, D68.3
Labile INR	1	Not applicable
Elderly > 65 years	1	
Drugs or alcohol concomitantly	1	Antiplatelet agents, NSAIDs
	1	Alcoholism: E24.4, F10, G31.2, G62.1, G72.1, I42.6, K29.2, K70, K86.0, O35.4, R78.0, T51.0, X45, X65, Y15, Y90, Y91, Z71.4, Z72.1

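### The active-cancer definition has no route for known metastatic disease, so some metastatic patients diagnosed more than 6 months earlier and untreated since are filed as non-cancer VTE and kept in the Phase II comparison

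*Protocol*

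**What the plan says.** Active cancer is defined in Protocol Section 4 (additional exclusion criteria: "Had a record of active cancer, defined as first diagnosis of cancer with V code"), the Figure 1 note in Section 9.1 and Section 9.2.2 item 7. The SAP repeats it in the Figure 1 note of Section 8.1 and in Section 8.3.2 item 7. There are two routes, both tied to the 6 months before the index date:

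- Route 1, in the fuller wording of Protocol 9.2.2: "Had a record of active cancer, defined as first diagnosis of cancer (ICD-10: C00-C97 [excluding non-melanoma skin cancer: C44]) with V code".
- Route 2: "receiving anti-cancer treatment (chemotherapy, radiation therapy, or cancer-related surgery) under cancer diagnosis with V code within the past 6 months period prior to index date".

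Recurrent or metastatic disease appears only in the parenthesis that explains how long the V code runs: "for reimbursement for 5 years or longer if recurrent/metastatic" in the Protocol abstract and "reimbursement for 5 years or longer if recurrent/metastasis" in SAP 8.3.2. It describes the code and qualifies nobody.

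The definition is used twice. In Phase I, "Descriptive analysis will be conducted separately in two cohorts of non-cancer VTE and cancer VTE patients according to co-presence of active cancer". In Phase II it is the only cancer exclusion. The SAP already identifies metastatic disease elsewhere: its Charlson table in Section 8.4 lists "Metastatic solid tumor" (C77-C80) with 6 points, measured in the 6 months before index.

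**The concern.** The purpose of exclusion 7 is to keep active cancer out of the NOAC-warfarin comparison, and the purpose of the Phase I split is to describe cancer and non-cancer VTE separately. A definition that can be missed by a patient with known metastatic disease works against both. Such patients would enter the SAP tables for patients without active cancer (1, 3, 5, 7, 9 and 11), of which 5 and 7 report death, discontinuation and 3- and 6-month persistence. They would also enter all four Phase II hazard ratios. The codes needed to find them are already in the plan.

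**Working it through.** **Step 1. Apply the two routes to each type of V-coded metastatic patient.**

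- First cancer diagnosis within 6 months of index, untreated: caught by route 1.
- First diagnosis more than 6 months before index, listed treatment in the window: caught by route 2.
- First diagnosis more than 6 months before index, no listed treatment in the window: caught by neither.
- Older primary, with a C77-C80 code first appearing in the window and no listed treatment: undecided. C77-C80 lies inside C00-C97, and the text does not say whether a first diagnosis is counted per patient or per code. The plain reading is per patient, and then neither route applies.

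**Step 2. How wide is route 2?** Protocol Table 1 counts "L01-04, H02AB02, H02AB04, H02AB06, H02AB07, H02AB09" as chemotherapy, and adds radiation, cancer surgery and haemopoietic cell transplantation. Protocol 9.3 lists H02 as corticosteroids, so a listed steroid given under a V-coded diagnosis is enough. The missed group is therefore limited to patients with none of these in the window.

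**Step 3. What does Phase II adjust for?** The propensity score covariates include the Charlson score and non-active cancer history (Protocol 9.3, SAP 8.4). Charlson enters SAP Tables 13-16 as a mean score. Six points from a metastatic tumour look the same as renal disease (2) plus complicated diabetes (2) plus hemiplegia (2). The cancer-history flag does not separate a cured tumour from current metastases, and its lifetime look-back can reach only to 1 Mar 2012, when the data start. Tables 13-16 have no metastatic row, and no listed sensitivity analysis varies the cancer definition. Adjustment is partial.

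**Step 4. Possible effect on the hazard ratio before adjustment.** Let f1 and f0 be the group's share of NOAC and warfarin users, and k its bleeding hazard relative to other patients. The factor on the NOAC-warfarin hazard ratio is about (1 + f1(k-1)) / (1 + f0(k-1)). None of these inputs is in the documents; all are assumed.

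| f1 (NOAC) | f0 (warfarin) | k = 1.5 | k = 3 |
|---|---|---|---|
| 1% | 1% | 1.000 | 1.000 |
| 1% | 2% | 0.995 | 0.981 |
| 2% | 1% | 1.005 | 1.020 |
| 1% | 5% | 0.980 | 0.927 |
| 5% | 1% | 1.020 | 1.078 |

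For example, 1% against 5% with k = 3 gives 1.02/1.10 = 0.927.

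**Step 5. Would removing the group cost power?** First the plan's own figure, for apixaban against warfarin at HR 0.75, two-sided 5%, 80% power, apixaban share 39.3% and event probability 1.19% (Protocol 9.5):

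- Events = (1.960 + 0.842)² / (0.393 × 0.607 × (ln 0.75)²) = 397.6.
- N = 397.6 / 0.0119 = 33,409, against 33,340 stated. The figure reproduces.
- With the projected 49,224 patients, power is 92.5%. Removing an assumed 1%, 2%, 5% or 10% gives 92.3%, 92.0%, 91.2% or 89.7%.
- Dabigatran is the tightest comparison: 36,162 × 0.90 = 32,546 patients remain, against 29,071 required.

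These figures take the plan's projected totals at face value and ignore the loss of precision from weighting. They show only that the exclusion itself is not a power problem.

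**The case against.** The strongest reply is that the definition is explicit, identical in both documents and broad in its treatment route, and that the retained patients are neither hidden nor unadjusted for. The SAP tables are titled as patients without active cancer, they report cancer history and the Charlson score, and Phase II balance is checked against an absolute standardized difference of 0.1. Much of this stands, and it rules out three stronger readings that a reader might infer:

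- That metastatic patients on supportive care are generally missed. Route 2 accepts any L01-L04 drug or a listed corticosteroid under a V code, so many of them are caught.
- That every newly coded metastasis fails route 1. The text leaves this open; it is an ambiguity to settle.
- That the hazard ratios are biased in favour of the NOACs. Nothing in the documents says that warfarin users hold more of these patients, and nothing gives their bleeding hazard or the residual after weighting.

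The reply does not close the gap for patients first diagnosed more than 6 months earlier and untreated in the window. It also has no answer for Phase I, where no propensity score is used and the cohort label is itself the result.

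**Conclusion.** The gap is certain on the text. Patients with V-coded metastatic cancer first diagnosed more than 6 months before index, with no listed treatment in the window, are labelled non-cancer in Phase I and kept in Phase II.

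The consequence is of unknown and probably small size. In Phase II what is shown is misclassification and retention. A distortion of the hazard ratio in either direction is possible, with an unadjusted factor of roughly 0.93 to 1.08 if the shares are 1% in one arm and 2% to 5% in the other and the hazard is 1.5 to 3 times higher. It is 1.00 with equal shares, and partial adjustment should bring it closer to 1. In Phase I the misfiled patients feed unadjusted into the death, discontinuation and persistence figures of the cohort without active cancer. It is worth correcting because the correction is cheap, but it does not threaten the validity of the study.

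**What to change.** 1. In each place where active cancer is defined (Protocol Section 4, Figure 1 note and 9.2.2 item 7; SAP Figure 1 note and 8.3.2 item 7), add a third route: or any secondary-malignancy code (C77-C80) recorded with a V code within the 6 months before the index date. Apply it to both the Phase I split and the Phase II exclusion.
2. State whether a first diagnosis is counted per patient or per code.
3. Keep the active-cancer event in SAP 8.4 consistent. It uses a V-coded C00-C97 code that is new within 5 years, with no treatment route, and is counted only among patients without active cancer.
4. Report the number reclassified per arm.
5. If Phase I has already been run (Protocol Section 6 planned preliminary results for 3Q 2021, before this version), at minimum prespecify a Phase II sensitivity analysis that excludes these patients.

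**Cost.** The programming is small and uses data already requested, but a changed Phase I split means re-running SAP Tables 1-12. A few patients in remission who still carry the code would move to active cancer. Local or haematological recurrences coded only to the primary site would still be missed, so the added route should be described as covering metastatic disease and not recurrence in general.
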